Of particular relevance to this application are the burdens associated with standard rTMS therapy. Current rTMS protocols for depression require daily sessions, each taking 45 minutes – for up to 6-8 weeks (O'Reardon et al., 2007). In our clinic this has imposed a significant burden on Veterans, as they attempt to balance treatment requirements with re-integration into society, family needs and cope with other stressors. Moreover, the trend in PTSD rTMS protocol development is to increase the number of pulses and treatment sessions to improve outcomes, supported by evidence showing a positive relationship between symptom improvement and number of pulses delivered (Karsen et al., 2014). From this perspective, future “conventional” rTMS protocols for PTSD will be longer and carry an increased treatment burden for Veterans.

Taken together, research on non-invasive brain stimulation for PTSD remains in its early stages, and it is critical to develop novel interventions that a) use an individual biomarker to select the treatment frequency, b) reduce the burden of care on Veterans, and c) addresses the common comorbidity of PTSD and depressive symptoms. This poises the synchronized TMS (sTMS, NeoSync Inc.) device to potentially revolutionize the treatment of PTSD with non-invasive stimulation. This is additionally informed by our own preliminary work in patients with PTSD and comorbid depressive symptoms, where we have found their IAF approximates those found in the general population (mean IAF of 9.58 ± 1.1 , $n = 18$, unpublished data), suggesting that sTMS synchronized to the alpha range will also be feasible in the population under study.

With these considerations in mind, we propose a small, two-site, sham-controlled pilot study of sTMS in patients with comorbid PTSD and depressive symptoms. We hypothesize that sTMS will be effective for PTSD and mood symptoms in this sample.

III. Experimental Methods

1. Brief Description of Subjects

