Subjects will be outpatients who meet the DSM-V criteria for PTSD (acute or chronic, confirmed by the Clinician Administered PTSD Scale [CAPS] and at least moderate severity, defined as score > 33 on the PTSD checklist [PCL-5]) and have at least moderate symptoms of depression (defined by moderate symptoms, or score ≥ 11 on the Quick Inventory for Depressive Symptomatology – Subject Rated [QIDS-SR]) and are 18 to 70 years of age (inclusive). Up to 35 participants will complete the study at the two sites, the Providence VAMC (Providence, RI) and the White River Junction VAMC (White River Junction, VT). Eligible subjects must provide written informed consent, be capable of comprehending the nature of the study, and be considered by the Investigator as likely to comply with the visit schedule. Additional inclusion/exclusion criteria are listed below.

2. Study Design

This study is a prospective, sham-controlled, trial of sTMS delivered to patients who are symptomatic despite ongoing pharmacotherapy for PTSD and mood symptoms. Serial self-report symptom assessments will take place at screening/baseline and weekly during the 4

weeks of the study. The treatment course will comprise a total of 20 double-blind treatment sessions. Treatments windows will be 10 calendar days to complete 5 treatments, with a 40-day window in total to complete 20 treatments. Post-treatment assessment sessions will take place on the last day of treatment, and again 1 month after the final treatment.

All veterans who complete the sham-controlled series will be offered open-label continuation treatment following the same administration structure (i.e., 20 open-label treatment sessions, with 10 calendar days to complete 5 treatments, within a 40-day window for all 20 treatments), with a 1-month, post-treatment visit). Of note, for patients who continue in open-label participation, the 1 final study visit (PT2, below) will occur 1 month after the final open label treatment.

3. Specific Procedures or Treatments

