We aim to maximize power through collaborative analyses including data collected from the two sites of the study. De-identified data will be shared for final analyses. At least 20 subjects will be completed in total. The sample size for this pilot controlled study is based on estimations regarding the appropriate amount of information required to inform next steps in trial design rather than on statistical significance calculations for any primary safety or efficacy endpoint. Previous studies of different TMS parameters for PTSD (without comorbid MDD) have utilized sample sizes of ~ N = 20. By employing a comparable sample size we anticipate having sufficient power to detect significant differences between baseline and endpoint. This sample size will be adequate to determine the appropriate sample size for a subsequent trial.

For the primary efficacy endpoint, we will analyze change in total scores on both PCL-5 scores from baseline to end point PT1. Categorical response (empirically defined as 50% decrease from pre-treatment baseline) and remission (below threshold score, per published standards for each scale) will be calculated for each scale, and these will be reported in a descriptive manner for the sample. Secondary efficacy endpoints will utilize pre- and post-treatment scores on the self-report scales and CAPS. Open-label results, potentially informing issues related to duration of treatment, will be reported descriptively.

IV. Material Inducements

Participants will be offered payments in the form of gift cards, for completion of three milestones in the study: \$25 giftcard for completion of all baseline procedures, \$25 giftcard for completion of all PT1 procedures, and \$50 giftcard for completion of PT2 procedures. There is a maximum total payment of \$100 to offset time and travel expenses incurred as a result of participation in the research assessments that are not standard of care for non-research patients who undergo sTMS therapy. Participants who undergo open-label treatment will receive an additional \$25 for completing OL PT1 procedures, bringing the maximum total of \$125

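### The power statement covers change from baseline, not active against sham, and no active-sham efficacy estimate is named (minor)

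*Combined protocol and SAP*

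**What the plan says.** Section II (Background) describes the trial in these words: "we propose a small, two-site, sham-controlled pilot study of sTMS". Section I gives safety and efficacy in a sham-controlled pilot as its first aim, and section III.2 (Study Design) specifies a sham-controlled course of 20 double-blind sessions.

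Section III.4 (Power Calculations and Data Analysis) sets a floor: "At least 20 subjects will be completed in total". Section III.1 sets a ceiling: "Up to 35 participants will complete the study at the two sites". Section III.4 bases the size on the information needed to plan next steps, "rather than on statistical significance calculations for any primary safety or efficacy endpoint". The one number it then offers is a precedent: "Previous studies of different TMS parameters for PTSD (without comorbid MDD) have utilized sample sizes of ~ N = 20". Two statements follow.

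- The first concerns power: "By employing a comparable sample size we anticipate having sufficient power to detect significant differences between baseline and endpoint".
- The second concerns planning of the next study: "This sample size will be adequate to determine the appropriate sample size for a subsequent trial".

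The primary endpoint is given as: "For the primary efficacy endpoint, we will analyze change in total scores on both PCL-5 scores from baseline to end point PT1". Response and remission are to be described for the sample, secondary endpoints use scores before and after treatment, and open-label results are descriptive. Nowhere do the documents define an efficacy quantity as a difference between active and sham.

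**The concern.** A pilot need not have a formal power calculation, and section III.4 openly says that it has none. The difficulty is the sentence that follows. It anticipates sufficient power without giving an effect size, SD, significance level or target power, and the contrast it refers to is baseline against endpoint.

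That contrast does not answer the trial's first aim. Patients selected for being symptomatic can improve through sham response or the passage of time, and a pre-post test counts all of that as change. This is so whether the arms are pooled or the test is run within the active arm; the section does not say which is meant. Because the endpoint sentence also leaves out an arm comparison, the plan could be followed to the letter and yield a significant change that says nothing about the device. Nor is the reader told how poorly a trial of this size would resolve the comparison the sham arm is there to provide.

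**Working it through.** **Plan's own figure.** There is none to reproduce. The documents give no numerical power, significance level, SD, target effect or allocation ratio.

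**Inputs from the documents.** 20 completers (section III.4) and 35 completers (section III.1).

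**Assumptions, not in the documents.** 1:1 allocation (10 and 10, or 17 and 18), two-sided 0.05, unadjusted t-tests, normal data, effects in SDs of the change score. The documents give no figure for PCL-5 improvement under sham, so 0.5 and 0.8 SD are used as a range.

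**Step 1. Pre-post test when the device does nothing.** Both arms improve by the same d. The paired t-test has n − 1 degrees of freedom and noncentrality d√n. For example, n = 20 and d = 0.5 give 0.5 × √20 = 2.236 against a critical value of 2.093, and a probability of 56%.

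| Test | n | d = 0.5 | d = 0.8 |
|---|---|---|---|
| Arms pooled | 20 | 56% | 92% |
| Active arm only | 10 | 29% | 62% |
| Arms pooled | 35 | 82% | >99% |
| Active arm only | 17–18 | 49–52% | 87–89% |

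In the same setting an active-sham test is significant in 5% of trials, by construction.

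**Step 2. Power of the active-sham comparison.** The two-sample t-test has n₁ + n₂ − 2 degrees of freedom and noncentrality d / √(1/n₁ + 1/n₂). For 10 and 10, √(1/10 + 1/10) = 0.447, so d = 0.8 gives 0.8 / 0.447 = 1.789 against a critical value of 2.101, and power of 40%.

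| True difference (SD) | 10 and 10 | 17 and 18 |
|---|---|---|
| 0.5 | 19% | 30% |
| 0.8 | 40% | 63% |
| 1.0 | 56% | 82% |
| Detectable at 80% power | 1.32 SD | 0.98 SD |

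The pre-post change detectable at 80% power with 20 completers is 0.66 SD pooled, or 1.00 SD in an arm of 10. The power sentence may therefore be reasonable for its own contrast.

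**Step 3. Precision of the active-sham difference.** The half-width of the 95% CI is t(0.975, df) × √(1/n₁ + 1/n₂) observed SDs.

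- 10 and 10: 2.101 × 0.447 = 0.94 SD.
- 17 and 18: 2.035 × 0.338 = 0.69 SD.

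**Step 4. Precision of the pilot SD.** The 95% CI for the pooled variance runs from df/χ²(0.975) to df/χ²(0.025) times the estimate: 0.57 to 2.19 with 18 df, and 0.65 to 1.73 with 33 df. For a fixed target difference, the size of a next trial scales with the variance and so carries the same factors.

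**The case against.** The sponsor can fairly say that this is a pilot, that the plan disclaims significance-based sizing, and that the precedent of about 20 is not its only rationale, since the section also appeals to the amount of information needed for trial design. That stands in part: the rationale exists but is not quantified, so the fair criticism is lack of quantified support rather than lack of any basis.

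The sponsor can also say that change from baseline is the variable an arm comparison would use, and that a controlled, double-blind design implies such a comparison. A reader might infer from the endpoint sentence that a pooled pre-post test is planned as the test of efficacy. The documents do not support that reading: the sentence names a variable and prescribes no test. The omission remains, because no other section supplies the comparison.

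A reader might also take the 92% as the expected rate of misleading results. It is the top of a range that rests on an assumed improvement and on pooling.

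Nor do the documents show that the size is inadequate for planning the next trial. They set no tolerance for adequacy, so Step 4 shows how uncertain the pilot SD would be without contradicting the plan's statement. That sentence alone would not justify a finding.

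Finally, section II cites a pooled effect for rTMS in PTSD of g = 2.67 (CI 1.11 to 4.23), which would make 10 per arm ample. Section III.4 does not use it, it concerns rTMS rather than sTMS, and section II itself cautions that it rests on 3 of 8 trials. At the lower limit of 1.11, power with 10 per arm is 65%.

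**Conclusion.** The concern holds, as a minor point. Section III.4 anticipates sufficient power, without quantified support, for a contrast that leaves out the sham arm, and the plan names no active-sham efficacy estimate for a sham-controlled trial. No printed figure is wrong, and a missing formal power calculation is not the fault.

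The figures in the working show scale only. They depend on the assumed allocation, significance level and test, and Step 1 also on the assumed common improvement. The omission itself depends on none of these: it follows from reading the sections together.

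**What to change.** 1. Replace the primary endpoint sentence in section III.4 with: *The primary efficacy estimate is the active-minus-sham difference in PCL-5 change from baseline to PT1, reported with its 95% CI; within-arm pre-post changes are descriptive.*
2. Delete the power sentence. Alternatively, limit it to within-subject change and add that it does not compare active with sham and that the trial is not sized to test efficacy against sham.
3. State the allocation ratio, then give the expected CI half-width with its assumptions labelled. If allocation is 1:1 and the interval is unadjusted and t-based, this is about 0.94 SD with 10 per arm and 0.69 SD with 17 to 18 per arm.

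An optional clarity edit is to replace the bare adequacy statement with a commitment to report the pilot SD and its CI.

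The cost is a less favourable stated claim and a wide interval, which must not be read as evidence of no effect. PCL-5 is already scheduled at screening/baseline and PT1 (Table 1), so no patients, visits or assessments are added.

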A. Screening: Patients who call in response to advertisements for the study or are referred by clinicians and meet preliminary demographic eligibility criteria upon phone screen will be invited to the clinic for a screening visit. Participants will also be drawn from clinical and research clinics at participating sites. After providing written informed consent, psychiatric interview and self-report measures will be used to confirm eligibility with regard to diagnosis, past psychotropic treatment history, current health history, and current symptom severity. The requirement for maintenance on a stable regimen of psychotropic medications for 6 weeks prior to baseline and during participation in the course of sTMS will be discussed.

B. Baseline/First Treatment Day: Patients meeting eligibility criteria will return within 2 weeks to begin the treatment protocol. Consent will be reviewed and confirmed with standard-of-practice forms for each institution. If indicated, women will be given a pregnancy test to make sure they are not pregnant. Clinical assessments will be updated (if more than 2 weeks have passed since screening visit), and data regarding functioning and quality of life will be collected with standardized measures. sTMS delivery will be calibrated using standard NeoSync procedures found in the device's user manual.

C. Serial Assessments: In the table below, PT1 refers to the assessment after the final sTMS treatment (i.e., after week 4 of the sham-controlled phase and, if relevant, after week 8 of the open-label phase). PT2 refers to the assessment completed 1 month after the final treatment (sham-controlled or open-label). PT1 and PT2 will include a psychiatric interview with the study PI or their designee. SC= screening visit, BL=Baseline/first treatment day, OL = open-label, with brackets indicating procedures done only in patients participating in the OL continuation phase. End-of-treatment week assessments are listed according to number of weeks of sTMS therapy completed by the time of assessment. * Indicates repeat evaluation at baseline if more than two weeks has passed since screening. Note that psychiatric assessments will occur at SC/BL, PT1, [OL PT1,] and PT2.

Table 1: Serial Assessments

Abbrev:	Assessment Title:	Administered at:
CAPS	Clinician Administered PTSD Scale	SC, BL*, PT1, [OL PT1,] PT2
CTQ	Childhood Trauma Questionnaire	SC, BL*
CGI-S	Clinical Global Impression - Severity	SC, BL*, PT1, [OL PT1,] PT2

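### The analysis section of this sham-controlled pilot commits to no active-versus-sham comparison, and its only power claim is for baseline versus endpoint

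*Combined protocol and SAP*

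**What the plan says.** Section I (aim i), the end of section II and section III.2 describe a two-site, sham-controlled pilot of efficacy and safety, with 20 double-blind sessions followed by optional open-label treatment.

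Section III.4 is the only place where an analysis is described:

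- Primary: "For the primary efficacy endpoint, we will analyze change in total scores on both PCL-5 scores from baseline to end point PT1".
- Response and remission, calculated for each scale: "these will be reported in a descriptive manner for the sample".
- Secondary: "Secondary efficacy endpoints will utilize pre- and post-treatment scores on the self-report scales and CAPS".
- Open-label phase: "Open-label results, potentially informing issues related to duration of treatment, will be reported descriptively".
- Basis of sample size: "The sample size for this pilot controlled study is based on estimations regarding the appropriate amount of information required to inform next steps", and not significance calculations for any primary endpoint.
- Power: "By employing a comparable sample size we anticipate having sufficient power to detect significant differences between baseline and endpoint".
- Use of the result: "This sample size will be adequate to determine the appropriate sample size for a subsequent trial".

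The section gives at least 20 completers in total; sections III.1 and VI.1 give up to 35. There is no number per arm, allocation ratio, alpha, SD, test or model.

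**The concern.** A sham arm and blinding exist so that active treatment can be compared with sham. Section III.4 never names that comparison, and no other section supplies it. Where it does name a contrast, in the power sentence, the contrast is baseline against endpoint.

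Two things are at stake. First, an analysis that follows the text could be purely pre-post. Improvement from baseline mixes any device effect with sham response and regression to the mean. The latter is a live issue because section III.1 admits only people above severity thresholds (PCL-5 above 33, QIDS-SR at least 11). Second, with no contrast fixed, the choice between a pre-post and a between-arm headline could be made after the data are seen. The plan also expects the pilot to inform the size of a later trial. If that trial is sham-controlled, sizing it needs a between-arm estimate and its variability, and the plan commits to neither.

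**Working it through.** **Text check.** Set beside the sham-controlled design, each efficacy statement in section III.4 falls short in the same way. The primary gives a variable (PCL-5 change) and a time point, but no arms. Response and remission are for the whole sample. The secondaries use scores before and after treatment. The power sentence concerns change over time. The section never mentions active, sham, arm or a between-group difference. This omission needs no arithmetic.

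**Does the power claim carry over?** The plan gives no numeric power, so there is no figure to reproduce. Its N of about 20 rests on the size of earlier studies.

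From the plan: N = 20 (minimum) and N = 35 (maximum), both in completers. Assumed, because the documents give none of these: two-sided alpha 5%, 80% power, 1:1 allocation (10+10 or 17+18), no dropout, effects in SD of the change score.

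Pooled pre-post change: one-sample t-test, df = N − 1, noncentrality d√N. The noncentrality needed for 80% power is 2.954 (df 19) or 2.884 (df 34).
- N=20: d = 2.954/√20 = 0.66
- N=35: d = 2.884/√35 = 0.49

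Active minus sham, unadjusted change scores: two-sample t-test, df = N − 2, noncentrality d/√(1/n1 + 1/n2). The noncentrality needed is 2.963 (df 18) or 2.886 (df 33).
- 10+10: √(1/10 + 1/10) = 0.4472; d = 2.963 × 0.4472 = 1.32
- 17+18: √(1/17 + 1/18) = 0.3382; d = 2.886 × 0.3382 = 0.98

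95% CI half-width of the difference, t(0.975, N − 2) × √(1/n1 + 1/n2):
- 10+10: 2.101 × 0.4472 = 0.94 SD
- 17+18: 2.035 × 0.3382 = 0.69 SD

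| | N=20 | N=35 |
|---|---|---|
| Detectable, pooled pre-post | 0.66 SD | 0.49 SD |
| Detectable, active minus sham | 1.32 SD | 0.98 SD |
| Power at 0.8 SD, pooled pre-post | 92% | over 99% |
| Power at 0.8 SD, active minus sham | 40% | 63% |

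The between-arm comparison needs an effect about twice as large (1.32/0.66 and 0.98/0.49 are both 2.0).

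**Adjusting for baseline.** Let r be the baseline–PT1 correlation and k the ratio of baseline SD to PT1 SD. With baseline balanced across arms, the residual SD as a fraction of the change-score SD is √[(1 − r²)/(1 + k² − 2rk)]. For r = 0.3 to 0.7 this runs from 0.806 to 0.922 at k = 1, and from 0.922 to 1.000 at k = 0.7. At df = N − 3 the noncentrality needed is 2.974 (df 17) or 2.889 (df 32), so the detectable effect before this factor is 2.974 × 0.4472 = 1.33 or 2.889 × 0.3382 = 0.98. Multiplying:
- k = 1: 1.07 to 1.23 SD at 10+10; 0.79 to 0.90 SD at 17+18
- k = 0.7: 1.23 to 1.33 SD at 10+10; 0.90 to 0.98 SD at 17+18

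The gain therefore depends on k as well as r. A k below 1 is plausible, because the PCL-5 entry threshold restricts the spread at baseline but not at PT1. Chance imbalance in baseline would raise these figures somewhat.

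**The case against.** The strongest reply is that the comparison is implied. The sample-size sentence calls this a controlled study, the primary is to be analysed while open-label results are only described, and change from baseline is an ordinary endpoint on which to compare arms. All of that is fair. A reader might infer that the sponsor plans to pool the arms or to drop the sham comparison; the documents do not say so. What stands is narrower: an endpoint is given, and the comparison to be made on it is not.

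A second reply is that this is a pilot whose size expressly does not rest on significance calculations. That answers any complaint that the trial is too small: low between-arm power breaches no stated target. It does not answer the missing contrast, and the same paragraph goes on to claim sufficient power.

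Three further inferences go too far:

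- That the sample can detect nothing but within-subject change. Section II quotes a pooled rTMS effect of g 2.67 (CI 1.11 to 4.23). If the lower limit is read as a between-arm effect in change-score SD (an assumption), unadjusted power at 1.11 is 65% at 10+10 and 89% at 17+18. Section II itself cautions that the meta-analysis rests on 3 of 8 trials.
- That PT1 is seriously ambiguous. Section III.3.C does define it as "after week 4 of the sham-controlled phase and, if relevant, after week 8 of the open-label phase", but Table 1 lists the open-label PT1 separately, and section III.4 makes open-label results descriptive.
- That a later trial will be sized on within-arm change. The plan does not say which estimate it would use.

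**Conclusion.** The concern holds as an omission. A sham-controlled efficacy aim has no specified active-versus-sham analysis, and the one power claim belongs to a different contrast. It should be corrected before analysis, because the primary, secondary and power statements, followed as written, allow a result that cannot isolate the device effect. This conclusion rests on the text alone and is held with high confidence.

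The size is illustrative: a detectable effect of 1.32 SD rather than 0.66 SD at the stated minimum, and 0.98 rather than 0.49 SD at the stated maximum, under the assumed alpha, power, allocation and absence of dropout. These figures show that the power statement does not transfer to the sham comparison. They do not show that the pilot is wrongly sized.

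**What to change.** In section III.4, state: *The primary efficacy analysis is the active-minus-sham difference in PCL-5 total at PT1 of the sham-controlled phase, adjusted for baseline PCL-5, with a 95% CI, by allocated arm.* An unadjusted comparison of change scores by arm would also cure the omission, and adjustment for site is optional. Naming the phase is tidying.

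Report response, remission and the secondary endpoints by arm, and keep within-arm change as descriptive.

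Confine the power sentence to within-subject change or delete it. Add that the sample was not sized for the active-minus-sham comparison, which will be interpreted by its estimate and CI. Do not replace it with a new assertion about what the sample is expected to detect. Any detectable effect quoted for an adjusted analysis should list its assumptions, including the baseline–PT1 correlation and the ratio of baseline to PT1 SD.

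The sponsor should confirm how participants are allocated, since the protocol text does not state a method or ratio.

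The cost is wording and that confirmation, with no added visits, measures or participants. The power statement becomes less favourable and the CI will be wide: about ±0.94 SD at 10+10 and ±0.69 SD at 17+18 for the unadjusted comparison.

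### The primary PCL-5 analysis to PT1, in a sample counted by completion, leaves out early stoppers and their week 1-3 scores, which can overstate the baseline-to-endpoint change

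*Combined protocol and SAP*

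**What the plan says.** Section III.4 (Power Calculations and Data Analysis) defines the primary efficacy analysis: "we will analyze change in total scores on both PCL-5 scores from baseline to end point PT1". It adds nothing on which participants are included or what happens when PT1 is absent. Response and remission are to be calculated for each scale, and "these will be reported in a descriptive manner for the sample".

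The sample size is expressed in completion. Section III.4 has "At least 20 subjects will be completed in total". Section III.1 has "Up to 35 participants will complete the study at the two sites", and section VI.1 repeats the upper figure. No number to enrol, dropout allowance or definition of completion is given.

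PT1 timing appears in two places. Section III.2 says "Post-treatment assessment sessions will take place on the last day of treatment, and again 1 month after the final treatment". Section III.3.C says "PT1 refers to the assessment after the final sTMS treatment (i.e., after week 4 of the sham-controlled phase", with a parallel clause for the open-label phase. Table 1 schedules the PCL-5 at screening, baseline, weeks 1-3, PT1 and PT2, so weekly scores exist for anyone who starts. Section III.4 gives them no role in the primary analysis.

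The only text on a participant who leaves concerns revoked authorization (section VI, Further Detail of Protection Against Risks, B). It allows data already collected to be used and seeks vital status. It does not mention the PCL-5.

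**The concern.** A change to PT1 can be computed only for someone who has a PT1. With no other rule stated, the literal analysis drops anyone who stops before PT1, along with up to three weekly scores that show how that person was doing.

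The quantity most exposed is the within-person change. If those who improve least are likelier to stop, the mean change among those who remain is too favourable, and so is the response rate, even when both arms lose equal numbers. Section III.4 rests its power statement on baseline versus endpoint and says the trial will inform the size of the next one, so an inflated change could carry forward. Because the analysis set is not named, it could also be chosen after the data are seen.

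**Working it through.** The plan gives no stop rate, SD or expected change, so there is no figure of its own to reproduce. Everything below except the 20 and the 35 is assumed.

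**1. How many people are affected.** Starters needed = completers / (1 − r), rounded up.

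| Stopping r | Starters for 20 | Stoppers | Starters for 35 | Stoppers |
|---|---|---|---|---|
| 10% | 23 | 3 | 39 | 4 |
| 20% | 25 | 5 | 44 | 9 |
| 30% | 29 | 9 | 50 | 15 |

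**2. Response rate.** Suppose 8 responders among 20 with a PT1: 8/20 = 40%. If no stopper responded, the rate among all starters is 8/23 = 34.8%, 8/25 = 32.0% or 8/29 = 27.6%.

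**3. Mean change.** Simulation with 400,000 participants per setting. The true mean PCL-5 change is linear to −15 (active) or −10 (sham) at week 4. SDs at weeks 1-4 are 8, 11, 13 and 15, with correlation 0.8 to the power of the lag. Stopping after weeks 1-3 is logistic in the last weekly change. Slopes of 0.5 and 1.0 per 10 points less improvement multiply the odds of stopping by about 1.6 and 2.7.

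Mean change among those with a PT1, true mean −15:

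| Slope | 10% | 20% | 30% | Overstatement (points) |
|---|---|---|---|---|
| 0 | −15.02 | −14.99 | −14.96 | nil |
| 0.5 | −15.54 | −16.08 | −16.65 | 0.5 / 1.1 / 1.7 |
| 1.0 | −15.97 | −16.90 | −17.84 | 1.0 / 1.9 / 2.8 |

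At true mean −10 and slope 1.0 the means are −10.94, −11.96 and −12.87, an overstatement of 0.9, 2.0 and 2.9. The range over informative settings is therefore about 0.5 to 2.9 points.

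**4. Using the weekly scores.** Sequential regression on the weekly scores, with a stopper's PT1 left missing, gives −14.97 to −15.01 at true mean −15, within 0.1 point throughout. With 25 starters, a repeated-measures analysis matched or beat the completer analysis on total error, even when stopping was random.

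**5. Entering a discontinuation score as PT1.** Same model, true mean −15, stopping 10/20/30%: slope 0 gives −14.2/−13.5/−12.7; slope 0.5 gives −14.2/−13.3/−12.5; slope 1.0 gives −14.1/−13.2/−12.3. Improvement is understated by 0.8 to 2.7 points, even when stopping is random. With 30% random stopping in both arms, the active-sham difference falls from 5.0 to about 4.2. This is last observation carried forward in effect.

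**6. Active-sham difference, completers only.** Equal stopping with the same mechanism in both arms: a shift of about 0.1 point or less. With 30% stopping on active and 10% on sham (biases from the −15 runs): 1.67 − 0.52 = 1.2 at slope 0.5, and 2.84 − 1.00 = 1.8 at slope 1.0. With 30% in both arms but slope 1.0 on active and 0 on sham: 2.84 − 0 = about 2.8.

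**7. Scale.** SE of the mean change in 20 participants = 15/√20 = 3.4. SE of the arm difference with 10 per arm = 15 × √(2/10) = 6.7. The bias in the change is thus 0.5/3.4 = 0.15 to 2.9/3.4 = 0.85 of its own sampling error.

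**The case against.** This is a pilot sized for information rather than significance, with descriptive response and remission rates. The stop rates are assumed, and the bias stays below sampling error. All of that stands and limits the weight of the point, but it does not supply an analysis set for a declared primary endpoint.

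The near-zero bias in step 4 is partly built in: stopping was made to depend only on recorded scores, which is what the mixed model assumes. That is a real limit. If stopping depends on something unrecorded, the model will correct only part of the bias.

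Several stronger readings are tempting and not supported:

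- *Sections III.2 and III.3.C contradict each other on PT1.* Both anchor it to the last treatment. The reference to week 4 can be read as describing a full course, and the sentence "End-of-treatment week assessments are listed according to number of weeks of sTMS therapy completed by the time of assessment" concerns the end-of-week assessments. For an early stopper the text is ambiguous, not contradictory.
- *Heavy dropout is to be expected.* Section VI (Potential Risks, C) says the visit load may be inconvenient over up to 10 weeks, which is longer than the four-week blinded course. Against that stand open-label treatment for those who finish the blinded series, payments at PT1 and PT2, and screening for likely compliance. The open-label offer may keep weak improvers in.
- *The treatment windows define who is analysed.* Section III.2 says "Treatments windows will be 10 calendar days to complete 5 treatments, with a 40-day window in total to complete 20 treatments". The two limits agree (4 × 10 = 40 days), and neither is made a test for inclusion.
- *The active-sham difference is safe if both arms lose equal numbers.* Only if the mechanism of stopping is also the same (step 6).

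**Conclusion.** The point holds as a gap with a cheap and better alternative, and should be fixed. A reader might infer that the plan prescribes a completer analysis. It does not say so; that is only what follows when its one sentence is applied literally and nothing else is supplied.

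The size depends wholly on assumptions: 10-30% stopping, odds of stopping related to the last weekly score, and SD 15. It vanishes if no one stops or if stopping is unrelated to improvement. The documents do not show that bias will occur, nor in which arm.

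**What to change.** In section III.4, define the primary set as every participant assigned to active or sham who has a baseline PCL-5, analysed in the assigned arm. Analyse PCL-5 change with a repeated-measures mixed model on weeks 1-3 and PT1, with a simple covariance structure named in advance because about 20 participants will not support a rich one.

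In sections III.2 and III.3.C, say that early stoppers are asked for the PT1 PCL-5 at the scheduled end of the course: week 4, and at the latest day 40. A score taken at discontinuation is filed under the week in which it was taken, never as PT1. If PT1 is not obtained, it stays missing.

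Report response and remission out of all assigned, stating that a missing PT1 counts as non-response. Give the completer analysis as sensitivity.

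The cost is a few sentences and one follow-up questionnaire per early stopper: 3 to 9 at 20 completers, or 4 to 15 at 35, under 10-30% stopping. No new instrument is needed. The downsides are that the model assumes stopping depends on recorded scores, and that partly treated participants may dilute the effect. Comparison with the completer analysis shows how much the choice matters.
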